## **8.6. Genetics**

### **8.6.1. Specified Genetics**

Specified genetic analyses are not evaluated in this study.

CCI

## **8.7. Biomarkers**

CCI

### **8.7.2. Specified Gene Expression (RNA) Research**

Specified gene expression (RNA) research is not included in this study.

### **8.7.3. Specified Protein Research**

Specified protein research is not included in this study.

### **8.7.4. Specified Metabolomic Research**

Specified metabolomic research is not included in this study.

## **8.8. Immunogenicity Assessments**

Immunogenicity assessments are not included in this study.

## **8.9. Health Economics**

Health economics/medical resource utilization and health economics parameters are not evaluated in this study.

## **9. STATISTICAL CONSIDERATIONS**

Detailed methodology for summary and statistical analyses of the data collected in this study is outlined here and further detailed in the SAP, which will be maintained by the sponsor. The SAP may modify what is outlined in the protocol where appropriate; however, any major modifications of the primary endpoint definitions or their analyses will also be reflected in a protocol amendment.

### **9.1. Statistical Hypotheses**

No formal statistical hypothesis testing will be performed in this study.

### **9.2. Analysis Sets**

For purposes of analysis, the following analysis sets are defined:

Participant Analysis Set	Description
Enrolled	“Enrolled” means a participant’s, or their legally authorized representative’s, agreement to participate in a clinical study following completion of the informed consent process and assignment to study intervention. A participant will be considered enrolled if the informed consent is not withdrawn prior to participating in any study activity after screening. Potential participants who are screened for the purpose of determining eligibility for the study, but do not participate in the study, are not considered enrolled, unless otherwise specified by the protocol.
Safety analysis set	All participants assigned to study intervention and who take at least 1 dose of study intervention.

Participant Analysis Set	Description
PK Concentration Set	The PK concentration population is defined as all participants who received at least 1 dose of PF-07081532 and in whom at least 1 plasma concentration value is reported.
PK Parameter Set	The PK parameter analysis population is defined as all participants who received at least 1 dose of PF-07081532 and have at least 1 of the PK parameters of interest calculated.

### 9.3. Statistical Analyses

The SAP will be developed and finalized before any analyses are performed and will describe the analyses and procedures for accounting for missing, unused, and spurious data. This section is a summary of the planned statistical analyses of the primary and secondary endpoints.

#### 9.3.1. General Considerations

Endpoints will be reported and analyzed according to the hepatic function group that participants fall into based upon their Child-Pugh score at screening.

##### 9.3.1.1. Analyses for PK Endpoints

Natural log-transformed PK parameters will be analyzed using an ANOVA model including hepatic function group as fixed effect. Estimates of the adjusted means and of the adjusted mean differences (Test-Reference) with their corresponding 90% CIs will be obtained before being exponentiated to provide estimates of the adjusted geometric means and of the ratio of adjusted geometric means (Test/Reference).

#### 9.3.2. Primary Endpoint(s) Analysis

##### 9.3.2.1. Definition of Endpoint(s)

The plasma PK parameters for PF-07081532 following single dose administration will be derived from the concentration-time profiles as detailed in [Table 3](#). Actual PK sampling times will be used in the derivation of PK parameters. In the case that actual PK sampling times are not available, nominal PK sampling time will be used in the derivation of PK parameters. The fraction of PF-07081532 unbound in plasma (fu) will be determined by the analytical lab and reported for each participant.

**Table 3. Plasma PK Parameters**

Parameter	Definition	Method of Determination
AUC last	Area under the plasma concentration-time profile from time zero to the time of the last quantifiable concentration (C last )	Linear/Log trapezoidal method.
AUC inf*	Area under the plasma concentration-time profile from time zero extrapolated to infinite time	AUC last + (C last *  /k el ), where C last * is the predicted plasma concentration at the last quantifiable time point estimated from the log-linear regression analysis.
C max	Maximum plasma concentration	Observed directly from data.
CCI		
fu	Fraction of unbound drug in plasma	Cu/C (where Cu represents unbound concentration and C represents total concentration).
AUC last,u	Unbound AUC last	fu·AUC last .
AUC inf,u *	Unbound AUC inf	fu·AUC inf .
C max,u	Unbound C max	fu·C max .
CCI		

\* as data permit

### 9.3.2.2. Main Analytical Approach

The effect of varying degrees of hepatic impairment on PK parameters will be assessed by constructing 90% CIs around the estimated difference between each of the Test (hepatic impaired) groups and the Reference (without hepatic impairment) group. A one-way ANOVA will be used to compare the natural log transformed PF-07081532 AUCinf, Cmax, AUClast, fraction unbound (fu), and associated unbound parameters (AUCinf,u, Cmax,u, AUClast,u), as data permit, for each of the hepatic impairment groups (Test) to the group without hepatic impairment (Reference). Estimates of the adjusted mean differences (Test - Reference), and corresponding 90% confidence intervals, will be obtained from the model. These will be exponentiated to provide estimates of the ratio of adjusted geometric means (Test/Reference) and 90% confidence intervals for the ratios.

Individual PF-07081532 concentrations will be listed and summarized descriptively by nominal PK sampling time and hepatic function group. Individual participant and summary profiles of the concentration-time data (using actual and nominal times, respectively) will be plotted by hepatic function group for both total plasma PF-07081532 and unbound PF-07081532.

Box and whisker plots for individual PK parameters ( $AUC_{inf}$ ,  $AUC_{last}$ ,  $C_{max}$ ,  $f_u$ ,  $AUC_{inf,u}$ ,  $AUC_{last,u}$  and  $C_{max,u}$ ) will be constructed by hepatic function group and overlaid with geometric means. PK parameters of PF-07081532 will be summarized descriptively by hepatic function group. Unbound fraction ( $f_u$ ) will be listed and summarized descriptively by hepatic function group.

### **9.3.2.3. Supplementary Analyses**

Additional analysis using linear regression may be used to analyze the potential relationship between appropriate PK parameters (eg,  $AUC_{inf}$ ,  $AUC_{last}$ ,  $C_{max}$ ,  $f_u$ ,  $AUC_{inf,u}$ ,  $AUC_{last,u}$ ,  $C_{max,u}$ ) and hepatic function (eg, serum albumin concentration, PT or T bili). Plots of PK parameters (eg,  $AUC_{inf}$ ,  $AUC_{last}$ ,  $C_{max}$ ,  $f_u$ ,  $AUC_{inf,u}$ ,  $AUC_{last,u}$ ,  $C_{max,u}$ ) versus hepatic function will be constructed, with a regression line and 90% confidence region included. Estimates of the slope and intercept, together with a 90% CI, and the coefficient of determination (ie, R-squared and adj-R-squared) may be obtained from the model.

Additionally, as an exploratory analysis, age and body weight may be explored as additional covariates/factors in the models, as appropriate.

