## 3. OBJECTIVES AND ENDPOINTS

Objectives	Endpoints
Primary:	Primary:

To compare the PK of PF-07081532 following administration of a single oral dose in adult participants with varying degrees of hepatic impairment relative to age- and body weight-matched participants without hepatic impairment.

	

Plasma: <math>C_{max}</math>, <math>AUC_{inf}</math>, <math>AUC_{last}^*</math>, <math>fu</math>, <math>C_{max,u}</math>, <math>AUC_{inf,u}</math> and <math>AUC_{last,u}^*</math>, as data permit.

Secondary:	Secondary:

To evaluate the safety and tolerability of a single oral dose of PF-07081532 when administered to adult participants with varying degrees of hepatic impairment and in age- and body weight-matched participants without hepatic impairment.

	

Assessment of treatment emergent AEs, clinical laboratory abnormalities, vital signs, ECG parameters.

CCI	

Objectives	Endpoints
• CCI	[REDACTED]

\* AUClast and AUClast,u will be treated as primary endpoints if data do not permit robust estimation of AUCinf and AUCinf,u, otherwise they will be treated as tertiary endpoints.

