### Staged Enrollment of Study Groups

Participants will be dosed in a staged manner as follows:

- Participants with moderate and severe hepatic impairment (Groups 3 and 4) will be enrolled first.
- Recruitment of participants with mild hepatic impairment (Group 2) will initiate when approximately 50% of the participants across Groups 3 and 4 have been dosed.

*Sponsor approval is required before proceeding with recruitment of Group 2.*

- An average value for age and weight for the 3 hepatic impairment groups (Groups 2-4) will be determined, and participants without hepatic impairment (Group 1) will be recruited to match the average demographics (at a minimum, age and weight, and as much as practically possible gender) across the pooled Groups 2-4.
- Recruitment for healthy participants in Group 1 (without hepatic impairment) may start when approximately 75% of total participants across Groups 2-4 (ie, approximately 12-13 participants) have been dosed.

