#### **5.1.2. Additional Inclusion Criteria for Group 1 *Only* (without Hepatic Impairment)**

1. At screening, no clinically relevant abnormalities identified by a detailed medical history, complete PE, including BP and pulse rate measurement, 12-lead ECG and clinical laboratory tests, as assessed by the sponsor approved laboratory.
2. At screening, participants must meet the demographic-matching criteria, including:
  - A body weight that is within  $\pm 10$  kg of the average of the pooled hepatic impairment groups (Groups 2, 3, and 4), as provided by the sponsor;

- An age that is within  $\pm 5$  years of the average of the pooled hepatic impairment groups (Groups 2, 3, and 4), as provided by the sponsor;
- *Attempts will be made* to ensure that the male-to-female distribution in Group 1 is comparable to that in the pooled hepatic impairment groups (Groups 2, 3, and 4).

3. No known or suspected hepatic impairment, and meet **all** the following criteria at screening, as assessed by the sponsor approved laboratory, with a single repeat permitted to assess eligibility, if needed:

- ALT  $\leq$  ULN;
- AST  $\leq$  ULN;
- T bili  $\leq$  ULN;

**NOTE:** Participants with a history of Gilbert syndrome (and hence elevated T bili) are eligible provided direct bilirubin level is  $\leq$  ULN **plus** ALT and AST are  $\leq$  ULN **plus** alkaline phosphatase, hemoglobin, and reticulocyte count are all  $\leq$  ULN.

- Albumin  $\leq$  ULN;
- PT  $\leq$  ULN.

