2.1. Modifications to the Analysis Plan Described in the Protocol

Not Applicable

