6.1.1.1. Main Analysis

C_{max} , AUC_{inf} (if data permit), AUC_{last} , fu , $AUC_{inf,u}$, $AUC_{last,u}$ and $C_{max,u}$ will be listed, summarized descriptively and analyzed by group for participants in the PK parameter set (as defined in Section 4). Missing values will be handled as detailed in Section 5.3.

A one-way analysis of variance (ANOVA) described in Section 5.2.3, that includes all 4 groups in the same model, will be used to compare the natural log transformed of C_{max} , AUC_{inf} , AUC_{last} , fu , $AUC_{inf,u}$, $AUC_{last,u}$, and $C_{max,u}$ of PF-07081532 separately, for each of the hepatic impairment groups (Test, Groups 2, 3, 4) to the healthy normal hepatic function group (Reference, Group 1).

For summary statistics and median or mean plots by sampling time, the nominal PK sampling time will be used. For individual participant plots by time, the actual PK sampling time will be used. The plasma PK parameters of PF-07081532 for each group will be summarized as specified in Table 7 below.

Table 7. Summary statistics to be produced for Plasma PK Parameters of PF-07081532

Parameter	Summary Statistics
C_{max} , AUC_{inf}^* , AUC_{last} , fu , $AUC_{inf,u}^*$, $AUC_{last,u}$, and $C_{max,u}$	N, arithmetic mean, median, cv%, standard deviation, minimum, maximum, geometric mean and geometric cv%.

* if data permits

The following plots will be presented:

- *Box and whisker plots for individual PK parameters (AUC_{inf} , AUC_{last} , C_{max} , fu , $AUC_{inf,u}$, $AUC_{last,u}$ and $C_{max,u}$) will be constructed by group and overlaid with geometric means.*

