Appendix 1. Statistical Methodology Details

An example of SAS code for ANOVA:

```
proc mixed data = tab.pk;
  class group;
  model l&var = group /residual;
  lsmeans group/diff cl alpha=0.1;
  ods output lsmeans = lsmeans&var;
  ods output diffs=diffs&var;
run;
```

An example of SAS code for the PROC REG code for linear regression analyses:

```
proc reg data=tab.pk;
  model l&var=clcr/clb alpha=0.1;
  ods output ParameterEstimates = param&var;
  ods output FitStatistics = fit&var;
  ods output ANOVA = reg&var;
run;
```

An example of SAS code for stepwise regression with model selection using AIC:

```
proc glmselect data=tab.pk analysis plot=ALL;
  model pk_p = albumin age weight/ selection=stepwise (select = AIC stop = AIC)
    include=1 hierarchy=none showpvalues;
run;
```

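### Must an age- and weight-adjusted group model be fixed in advance because Group 1 is matched only to the pooled average of Groups 2-4?

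*Protocol*

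**What the plan says.** The primary objective (Protocol section 3) compares impaired participants "relative to age- and body weight-matched participants without hepatic impairment". The match is to one average. Under Staged Enrollment in Protocol 4.1, Group 1 "will be recruited to match the average demographics (at a minimum, age and weight", with gender as far as practicable) over Groups 2-4 together. Protocol 5.1.2 holds each Group 1 participant to within 10 kg and 5 years "of the average of the pooled hepatic impairment groups (Groups 2, 3, and 4), as provided by the sponsor".

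The main analysis has no covariates. Protocol 9.3.1.1: "Natural log-transformed PK parameters will be analyzed using an ANOVA model including hepatic function group as fixed effect". SAP 6.1.1.1 describes a one-way ANOVA "that includes all 4 groups in the same model, will be used to compare the natural log transformed" parameters, and the PROC MIXED code in SAP Appendix 1 contains group only.

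On adjustment, Protocol 9.3.2.3 says that "as an exploratory analysis, age and body weight may be explored as additional covariates/factors in the models, as appropriate". SAP 2.1, headed "Modifications to the Analysis Plan Described in the Protocol", is marked not applicable. The only visible SAP code with age and weight is the stepwise example in Appendix 1, "model pk_p = albumin age weight/ selection=stepwise", which keeps albumin in and selects by AIC. In the public copy, text is redacted after SAP 5.2.3, after SAP 5.2.4 and at the start of SAP 6.1.1.2.

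**The concern.** The design balances the pool, but the analysis reports each group. If the severe group is lighter than the pool and lighter people have higher exposure, part of the severe/Reference ratio reflects weight. The mild ratio could be off in the other direction. Nothing limits how far one group's mean may lie from the pooled average.

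The visible remedy is optional and gives no covariate scale, parameter list or trigger. The visible stepwise code has no group term, so it cannot produce an adjusted Test/Reference ratio. The study is open-label, and Protocol 9.4 lets the sponsor review data while it runs. Whether and how to adjust could therefore be settled after exposures and weights are known. The ratios are meant to inform dosing recommendations by degree of hepatic function (Protocol 2.3.2), so a misattributed weight effect would matter if it were large.

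**Working it through.** **Plan's own figure.** Four groups of 6 give 4 × 6 = 24, as Protocol 9.5 states. The SD of ln AUCinf and the limits in Table 4 are redacted, so the precision statement cannot be reproduced exactly. With an assumed SD, the half-width of the 90% CI on the ln scale (80% coverage probability, 20 residual df) is

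t(0.95, 20) × SD × √(1/6 + 1/6) × √(χ²(0.80, 20)/20), with t = 1.7247.

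| Assumed SD | Half-width (ln) | 90% CI around an estimated ratio of 2 |
|---|---|---|
| 0.3 | 0.334 | 1.43 to 2.79 |
| 0.4 | 0.446 | 1.28 to 3.12 |
| 0.5 | 0.557 | 1.15 to 3.49 |

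**Bias by direct arithmetic.** Assume exposure is proportional to weight^(−b), with b from 0.5 to 1. A Test group averaging 70 kg against a Reference at 80 kg gives a spurious ratio of (70/80)^(−b) = 1.07 to 1.14. A Test group at 90 kg gives 0.94 to 0.89. On the ln scale, 1.07 to 1.14 is about 0.07 to 0.13, against ln 2 = 0.693 and a half-width of 0.446 at SD 0.4.

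The pooled average contains the deviant group, which shrinks the gap. With group means of 88, 88 and 75 kg the pooled mean is 83.7 kg, so the severe group lies 8.7 kg from the target, not 13. For the Group 1 mean to lie 10 kg from that target, every member would have to sit at the individual limit.

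**Simulation, 40,000 trials per scenario.** All inputs are assumptions: 6 per group; nominal weights 75 kg in the severe group and 88 kg elsewhere, restricted to eligible weight and BMI; Group 1 within 10 kg and 5 years of the pooled average; b from 0.5 to 1; residual SD 0.3 to 0.5; true ratio 1. The adjusted model is group + age + ln(weight).

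- Unadjusted severe ratio: 1.03 to 1.10, with 90% CI coverage 0.86 to 0.90. Coverage of 0.86 arises only at b = 1, SD 0.3 and weight SD 12 kg.
- Adjusted severe ratio: 1.00, coverage 0.90.
- Age alone (severe group about 6 years younger, exposure rising 5 to 10% per decade): 0.96 to 0.98 unadjusted, which is opposite in direction to the weight effect.

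**Does adjustment give a better estimate?** Root mean squared error of the ln ratio, with matching to the final pooled average:

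| b | SD | Weight SD (kg) | ANOVA | Adjusted |
|---|---|---|---|---|
| 1 | 0.3 | 12 | 0.207 | 0.188 |
| 0.75 | 0.3 | 12 | 0.194 | 0.189 |
| 0.75 | 0.5 | 17 | 0.299 | 0.305 |
| 0.5 | 0.5 | 12 | 0.293 | 0.314 |

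It helps with a strong effect and a small SD, and hurts with a weak effect and a large SD.

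**Cost if the covariates do not matter (SD 0.3).** The half-width rises from 0.295 to between 0.305 and 0.322 with 6 severe participants (0.305/0.295 = 1.03; 0.322/0.295 = 1.09). With 4 it rises from 0.331 to between 0.347 and 0.370 (1.05 to 1.12).

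**Fluid in Group 4.** Protocol 5.2.3 allows severe ascites in Group 4 only. Assume 8 kg of fluid, with exposure following dry weight. If severe dry weight equals that of the other groups, the ANOVA ratio is 1.02 to 1.07 and the adjusted ratio 1.05 to 1.10, so adjustment makes it worse. If severe dry weight is 75 kg, 1.07 to 1.16 becomes 1.05 to 1.11, a partial correction.

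**Gap between the two models in one trial.** The median difference between the two severe ratios is 4 to 10%. It is already 3 to 7% when age and weight have no effect at all, so much of the gap is small-sample noise from fitting two covariates.

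**The case for a change.** The strongest case for a change is that the sponsor treats age and weight as factors to be controlled, writes matching into the primary objective, and allows up to two extra Group 1 participants to protect it. One prespecified sensitivity table would show what matching to the pool leaves uncorrected. It needs no new data, and it would close a choice that can otherwise be made with the data in view. By-group demographics (SAP 6.5.1) reveal an imbalance but not its effect on the ratios.

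The description of the matching and of the visible text stands. So does the point that the stepwise code yields no group ratio. The step to a needed change does not, for three reasons.

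- The reported ratio is not left open. The ANOVA is set out in both documents. Protocol section 9 requires an amendment for major changes to the primary analysis, 9.3 requires the SAP to be final before any analysis, and SAP 5.2.3 requires any alternative to the planned analysis to be justified in the report. Even if the larger of the two ratios were always reported, simulated coverage would be 0.862 to 0.896 against a nominal 0.90.
- The absence of a fixed model cannot be asserted. No visible SAP section describes the stepwise selection shown in Appendix 1, so the covariate text it serves presumably lies in the redacted blocks. What is redacted is not missing. The sentence in Protocol 9.3.2.3 also follows the paragraph on regressions against liver-function markers and may refer to those, in which case a stepwise model without a group term is deliberate.
- The adjusted model is not a safe reference for judging the ANOVA, least of all in Group 4, where an imbalance in weight is hardest to interpret.

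**Conclusion.** The concern describes the visible plan correctly but does not call for a change. What is open is the form of an exploratory analysis, a detail analysts can sensibly fill by adding age and ln(weight) to the group model and showing the result beside the ANOVA as supportive only, with Group 4 read cautiously. The one-way ANOVA remains a sound main analysis.

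In the simulated weight scenario the possible bias is about 3 to 10%. It is small against the 2-fold difference behind the sample size and against the width of the planned intervals. Protocol 9.1 and SAP 5.1 exclude hypothesis tests and decision rules, so no formal conclusion turns on it. Adjustment trades that bias for wider intervals and, in some settings, a larger error.

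This rests on assumed group weights, weight effect and SD, because the visible documents give none of them. Group means much further apart together with a strong weight effect would enlarge the bias, and the by-group demographic summary would show such an imbalance.

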### **9.3.3. Secondary Endpoint Analysis - Safety Analyses**

All safety analyses will be performed on the safety population.

AEs, ECGs, BP, pulse rate, and safety laboratory data will be reviewed and summarized on an ongoing basis during the study to evaluate the safety of participants. Any clinical laboratory, ECG, BP, and pulse rate abnormalities of potential clinical concern will be described. Safety data will be presented in tabular and/or graphical format and summarized descriptively, where appropriate.

Medical history and physical examination and neurological examination information, as applicable, collected during the course of the study, will be considered source data and will not be required to be reported, unless otherwise noted. However, any untoward findings identified on physical and/or neurological examinations conducted during the active collection period will be captured as AEs, if those findings meet the definition of an AE. Data collected at screening that are used for inclusion/exclusion criteria, such as laboratory data, ECGs, and vital signs, will be considered source data, and will not be required to be reported, unless otherwise noted. Demographic data collected at screening will be reported. COVID-19 specific assessments data will be considered source data and will not be required to be reported.

### 9.3.3.1. Electrocardiogram Analyses

Changes from baseline for the ECG parameters HR, QTcF, PR interval, and QRS complex will be summarized by treatment and time. The frequency of uncorrected QT values above 500 ms will be tabulated.

The number (%) of participants with maximum postdose QTcF values and maximum increases from baseline in the following categories will be tabulated by treatment:

